5.5 Data collection methods

5.5.1 *Patient Self-Assessed Frailty*: Patients will use the CFS to self-assess frailty at their clinical baseline, which measures nine distinct degrees of frailty from ‘managing well’ to ‘terminally ill’ (**Figure 1**). The wording in the CFS has been adapted and validated for patient-use (32).

5.5.2 *Patient Expectations of Health Care*: Patients will review and rank items on a standardized list of care interventions (i.e. pulmonary exercise programs, homecare, self-management education). The study team developed the list based on services recommended in Health Quality Ontario’s updated ‘Quality Standards for COPD’ document (38), and currently available community-based programs to help individuals with their functional, social, and lung health needs. The document will be written in lay language and a member of the research team will ensure items on the list are well understood by patient participants. Patient participants will rank each item on a likert scale from 1 (least important), to 5 (most important), to indicate their care preferences. ([COPD & Frailty - Baseline survey](#))

5.5.3 *Patient Baseline Health Data* (see **Data Collection Sheet – Baseline visit)**: We will collect variables from direct patient assessment and review of the electronic medical record at the time of recruitment:

- Socio-Demographic Data (age, sex, body mass index, physician-assessed clinical frailty scale score, current dwelling, caregiver support, marital status, education level, type of home assistance services, and duration of time since initial diagnosis).

- COPD-Specific Factors (Spirometry values (FEV1, FVC, FEV1/FVC), smoking history in pack-years, home-oxygen use, 6-minute walk test distance (if available), influenza and pneumococcal vaccination status, use of pulmonary rehabilitation, and number of flare-ups in the last year).
- General Health Data (co-morbidities, presence of family physician).
- Previous Health Service Utilization (hospitalizations, intensive care unit admissions, emergency room visits in last 1-year).

5.5.4 **Physician Data Collection:** We will ask the referring respirologist (in the patient's circle of care) to provide a frailty measurement at the time of study enrolment, using the CFS (Figure 1). This physician will also rank their desired care interventions for the patient using the same standardized list given to study participants (see [Recruitment Survey](#)).

5.5.5 **Frailty assessment by research team:** Frailty will be assessed during the 6-month and 12-month follow-up telephone visits, using the standardized CFS classification tree. ([Appendix 2](#))

5.6 Outcomes

5.6.1 **Primary:** The primary outcome is respiratory Health Related Quality of Life (HRQOL), as measured by the validated short version of St. Georges Respiratory Questionnaire (SGRQ-C) (39). The SGRQ-C is a 40-item questionnaire which generates an overall score between 1 and 100, with lower scores indicating better quality of life (39,40). The minimally important clinical difference in SGRQ-C scores is well established at 4 (41). The SGRQ is a widely used outcome in respiratory research, and there are established standard deviation measurements in the COPD patient population (42–44). These will be collected with the COPD & Frailty – baseline, 6-month, and 12-month surveys.

5.6.2 **Secondary:** We will measure burden of symptoms with the COPD Assessment Test (CAT) and the modified Medical Research Council (mMRC) scales (45,46). Both scales are validated and widely used in respiratory research. These will be collected with the COPD & Frailty – baseline, 6-month, and 12-month online surveys.

Psycho-social well being will be measured with the validated Generalized Anxiety Disorder (GAD)-7 and Patient Health Questionnaire (PHQ)-9 scales (47,48). The GAD-7 is a screen for generalized anxiety disorder, while the PHQ-9 scale measures the

presence of depressive symptoms in the prior two weeks (47–49) . Both scales are composed of seven items, based on the DSM-IV criteria, and a score above 7 on each scale will indicate the presence of anxiety or depression for this study (48,49). We will also collect outcomes of mortality, and health service utilization including hospitalizations (during study period), emergency room visits, and changes of dwelling to an assisted living environment. These will be collected with the COPD & Frailty – baseline, 6-month, and 12-month online surveys.

5.7 Statistical Methods:

5.7.1 ***Quantitative Analysis (Objective 1):*** The primary outcome (HRQOL using SGRQ-C scores) will be analyzed using multiple variable linear regression, with degree of frailty as the main predictor ('vulnerable', 'mildly frail', 'moderately frail', and 'severely/very severely frail'). Secondary outcomes for symptom burden (CAT and mMRC scales) and psycho-social wellbeing (GAD-7 and PHQ-9) will be described with median (IQR) statistics within each degree of frailty and analyzed with multiple variable linear regression to determine their associations with progressive degrees of frailty. Finally, the association between frailty and health service utilization (hospitalization, emergency room visit) and mortality will be analyzed with multivariable logistic regression. Potential confounding variables will be selected a-priori and forced into the model, regardless of statistical significance. Backwards selection will be used to obtain the most parsimonious model.

5.7.2 ***Quantitative Analysis (Objective 2):*** We will use descriptive statistics (proportions, means \pm SD, medians (IQR)) to characterize the ranked care expectations, socio-demographic, and disease-specific, variables. Variables will be stratified by physician-assessed degrees of frailty, and chi-square and ANOVA testing will be used to analyze differences in variables across degrees of frailty, for categorical and continuous variables, respectively.

5.7.3 ***Quantitative Analysis (Objective 3 & 4):*** We will calculate the percentage of agreement to assess inter-rater agreement between patients' self-assessed and physician-assessed frailty ratings at the baseline visit. This will be presented as a

cross-tabulation table. We will graph the trajectory of frailty rating between baseline, 6-month, and 12-month visits for the study cohort.

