6-month and 12-month follow-up visits: Prior to the scheduled 6-month or 12-month follow-up visit, the study team will send an e-mail to patient with a link to [the COPD & Frailty – 6-month follow-up survey](#) or [COPD & Frailty – 12-month follow-up survey](#). Patients who did not provide an e-mail address will receive an appointment reminder call from a member of the study team and complete the survey with the study team during their 6 and 12-months telephone follow-up visits. At the end of each telephone visit, patients will be asked to confirm their mailing address to send the second and third gift cards (of 20\$).

5.4 Sample Size: Sample size calculations were performed based on the primary analysis strategy, which uses multiple variable linear regression with a fixed model. We will determine the adjusted association between frailty (categorized in 4 groups using the CFS: ‘vulnerable’, ‘mildly frail’, ‘moderately frail’ and ‘severely/very severely frail’) and respiratory health-related quality of life as measured by the validated SGRQ-C, scored from 1-100. The minimally important clinical difference (MCID) for the SGRQ-C is 4 (41). We will adjust the model for confounding variables including age, sex, dyspnea severity (mMRC), hospitalization, lung function, home support services, and comorbidity scores.

In a previous sample of patients with COPD, the standard deviation of SGRQ scores ranged from 13 to 18 (9,42–44). To detect an effect size of 0.2 to 0.3, with 10 predictors and α error 0.05 and power 0.80 (1- β error), we require a range between 64 to 84 individuals (G*Power 3.1.9.2).

Copyright (C) 1992-2014, see **Appendix 1**.

Further, Harrell suggested that **10 subjects per variable** is the minimum required sample size for linear regression models. To ensure accurate prediction in subsequent study participants, we will need 100 individuals to include 10 predictors in our statistical model (50).

Based on the above calculations, we aim to recruit a minimum of **120** patients into this study over 6 months with a minimum of 30 patients in each of the four frailty categories vulnerable, mild, moderate, and severe/very severe. We will continue to recruit patients from the ambulatory clinic until the minimum targets are met.

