5.8 Data sources

- **Patient surveys:** For each study visit, patients will be asked to complete surveys relating to: CFS, SGRQ-C, mMRC Dyspnea Scale, CAT, GAD-7 and PHQ-9 .
- **Physician surveys:** CFS and care expectations for patient at time of enrolment
- **Electronic Medical Record:** Baseline health data, socio-demographic data, COPD-specific data, previous health care service utilization (1 year prior to study enrolment)
- **Baseline telephone visit with research team:** baseline health data, COPD specific data, previous health care service utilization.
- **6 & 12 month telephone visits with research team:** CFS, change in health status (stress event or falls) since last visit.

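### Deaths, hospitalisations, emergency visits and moves to assisted living have no stated follow-up source that works without a living, responding patient

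*Combined protocol and SAP*

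**What the plan says.** Section 5.6.2 lists the event outcomes: "We will also collect outcomes of mortality, and health service utilization including hospitalizations (during study period), emergency room visits", followed by moves to assisted living. The next sentence names the source: "These will be collected with the COPD & Frailty – baseline, 6-month, and 12-month online surveys".

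Section 5.3 gives the way round for patients without e-mail, who "complete the survey with the study team during their 6 and 12-months telephone follow-up visits". At baseline, staff go through the survey with any patient who has not completed it. At follow-up, that help is stated only for patients who gave no e-mail address.

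The other data sources are described as follows.

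- **Medical record.** Section 5.5.3 describes "review of the electronic medical record at the time of recruitment". Section 5.8 lists baseline data and "previous health care service utilization (1 year prior to study enrolment").
- **Follow-up calls.** Section 5.8 lists "CFS, change in health status (stress event or falls) since last visit".
- **Patient surveys.** Section 5.8 says "patients will be asked to complete surveys relating to: CFS, SGRQ-C, mMRC Dyspnea Scale, CAT, GAD-7 and PHQ-9". None of the event outcomes is on that list.
- **Physician surveys.** Section 5.8 places these at enrolment only.

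Section 5.7.1 plans multivariable logistic regression of hospitalisation, emergency visits and mortality on frailty. It gives no rule for patients whose status is unknown.

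**The concern.** The named source depends on the patient, and the outcomes are ones that remove patients from that source. Someone who has died returns no survey. Someone admitted, moved to care or too unwell to respond after month 6 may return none at month 12, and nothing in the text says how their later events would be found.

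Survival and health service use are part of the hypothesis in section 4.0, and service use is in Objective 1. The exposure is frailty, which section 2.0 links to death, poor recovery after admission and re-admission. It is therefore plausible that events are missed more often in some frailty categories than in others. That is a condition under which the planned odds ratios are biased.

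**Working it through.** **Step 1: can any stated source find an event in a patient who has died or stopped responding?**

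- Follow-up survey, online or by telephone: no, it needs the patient.
- 6- and 12-month calls: a stress event might include an admission, but only if the patient answers. Staff may learn of a death when a call fails; no procedure for recording it is stated.
- Medical record: it could, but its stated use is at recruitment and for the prior year.
- Retention measures (section 8.2): gift cards and personal contact may reduce loss. They do not find events in those already lost.

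**Step 2: the plan's own figures.** The documents give no event rate, drop-out rate or power figure for these outcomes, so there is nothing to reproduce on this point. The 64 to 84 patients in section 5.4 belong to the primary linear regression.

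**Step 3: illustration.** From section 5.4: at least 30 patients per frailty category, 120 in all. Assumed: 14 of 30 severe and 6 of 30 vulnerable patients are hospitalised.

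True odds ratio = (14/16)/(6/24) = 3.5.

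Missed events can enter the analysis in two ways. Let c be the share of events captured in a category.

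*(a) Patients with missed events drop out and event-free patients are all retained.* Observed odds ratio = true odds ratio × (c severe / c vulnerable).

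- Three severe events missed: (11/16)/(6/24) = 2.75.
- 70% captured in the severe group only: (9.8/16)/(6/24) = 2.45, a factor of 0.70.
- 70% captured in the vulnerable group only: (14/16)/(4.2/24) = 5.00, a factor of 1.43.
- Equal shares: a factor of 1.

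*(b) Patients with missed events stay in and are coded event-free, for example after a clean 6-month survey.* The missed events move into the non-event cell.

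- Three severe events missed: (11/19)/(6/24) = 2.32.
- 70% captured in the severe group only: (9.8/20.2)/(6/24) = 1.94, a factor of 0.55.
- 70% captured in the vulnerable group only: (14/16)/(4.2/25.8) = 5.375, a factor of 1.54.

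**Step 4: when there is no bias.** If 30% of severe patients drop out regardless of outcome, (9.8/11.2)/(6/24) = 3.5, which is unchanged. This protection belongs to mechanism (a). If those same patients were kept and coded event-free, the result would be the 1.94 above.

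These are crude odds ratios; adjusted models may differ.

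**The case against.** The strongest reply is that the source sentence in 5.6.2 is stock wording. Much the same sentence closes the primary outcome and both secondary paragraphs, and for mortality it even names the baseline survey. On that view the team never meant deaths to be self-reported and simply left its procedure unwritten. The survey forms and some parts of the protocol were not available and could contain one. This stands as a limit on the claim: what is shown is that no such source is stated in the text available. It does not remove the point, because an item on a form still cannot reach a patient who has died or stopped responding.

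A reader might infer three stronger things that the documents do not support.

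- *The study will record no deaths.* Staff may learn of deaths through scheduled calls, so a count of zero does not follow.
- *The surveys contain no service-use items, because section 5.8 lists none.* That list is incomplete. It also omits the care-preference rating, which section 5.5.2 places in the baseline survey ("Patient participants will rank each item on a likert scale from 1 (least important), to 5 (most important), to indicate their care preferences"). The two sections need aligning, but the omission is not proof of what the forms contain.
- *The frailty effect will be understated.* Attenuation is plausible, but step 3 shows that inflation is possible too.

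It is also fair to say that these are secondary outcomes. The primary SGRQ-C analysis and its sample size are not affected by this point.

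**Conclusion.** The point holds as a gap in a stated collection rule. The source named for mortality and service use needs a living, responding patient, and the text available gives no other follow-up source for outcomes that section 5.7.1 goes on to model. Where event capture differs by frailty category, bias can run either way. Under the assumptions above, with 70% capture in one group only, the odds ratio is multiplied by 0.70 or 1.43 if the affected patients drop out, and by 0.55 or 1.54 if they are coded event-free. The event counts and capture shares are illustrative, and the documents do not allow the actual size to be estimated. The change should be made, but it does not threaten the primary analysis.

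**What to change.** **Sections 5.6.2 and 5.8.** Add electronic medical record review at 6 and 12 months for every enrolled patient, whether or not they respond. It should cover vital status, hospitalisations, emergency visits and, where recorded, moves to assisted living, and be used together with self-report. When a call fails, establish vital status from the record or from a contact nominated at baseline, and record the date and source. List these items in 5.8 so that it agrees with 5.6.2.

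**Section 5.7.1.** Count a patient as event-free only if status is confirmed through month 12. A completed 6-month survey, or an encounter before month 12, does not confirm the later interval, and a silent hospital record does not prove that nothing happened. Report the number unconfirmed by frailty category. Dropping only the unconfirmed would keep non-responders with a recorded event and remove those without one, so add a sensitivity analysis that codes the unconfirmed first as event-free and then as having the event.

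**Cost.** Two brief chart checks for each of 120 patients (120 × 2 = 240), by staff who already review the record at recruitment; one nominated contact per patient; and possibly a change to consent or ethics wording, which could not be checked. Deaths at home and admissions elsewhere may still be partly missed.

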5.0 METHODS

5.1 Design & Setting: A prospective cohort study at The Ottawa Hospital (TOH) over two years. TOH is a quaternary care academic hospital with an ambulatory care respiratory clinic, staffed by seven respirologists. It is a regional referral center with a catchment area of approximately 1 million individuals.

5.2 Study population and Inclusion Criteria: We will include literate English or French-speaking outpatients with COPD, objectively confirmed by lung function testing¹. In patients with multiple respiratory conditions and comorbidities, COPD will be the primary diagnosis, as confirmed by the treating respirologist. Participants will be recruited from the respirology ambulatory care clinics at TOH. We will exclude patients with a known diagnosis of severe cognitive impairment², if the

¹ post-bronchodilator Forced Expiratory Volume in 1 second / Forced Vital Capacity ratio below the lower limit of normal, and >10 pack years history of tobacco smoking

² as per the medical record

recruiting physician feels the impairment would preclude participation in the study.

5.3 Study flow: Prior to the clinic, members of the study team (PI and coordinator) will review the list of patients scheduled for a routine visit in the Respirology clinic of TOH during the study period. Patients who have a diagnosis of COPD will be flagged as “identified” in EPIC for the study. The name (first and last) and MRN will be included in a Master List. This list will link patients’ identifiable information (MRN and name) with a screen ID. The screen ID will be included in an *“appointment note”* within the physician’s schedule in EPIC, flagging the care team that the patient is possibly eligible for the study.

[figure not shown]

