6.0 STUDY TIMELINE

- **Pre-implementation & Education of study staff and co-investigators** (December 2019 – February 2020):
 - Research Ethics Board application and study set-up
 - Prepare study documents (patient information sheets, physician reminders, poster of CFS) to increase awareness and reminder to enroll patients
 - Host session with respirologists from TOH General Campus to review how to use the CFS, review study process, and research plan
- **Hire** (February-April 2020):
 - Hire research assistant to assist with the collection of data.
 - Acquire equipment necessary for the study conduct (iPad, study laptop).
- **Implementation & Data Collection** (November 2022- March 2024):
 - Recruit patients from the Respirology outpatient clinic of TOH, General campus, obtain consent (November 2022 to March 2024)
 - Collect patient data (at baseline, 6 months, and 12-month follow-ups) with study staff.
- **Data Analysis** (March 2024):

- Quantitative data analysis performed by an OHRI methodologist from the Ottawa Hospital Performance Measurement team.
- **Knowledge Translation & Next Steps** (April 2024 and beyond):
 - Manuscript submissions and plan for next steps

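### Hospitalisation, emergency room visits and mortality are analysed as yes/no by logistic regression over an undefined period, with no allowance for time at risk or rule for patients who die, withdraw or are cut off early

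*Combined protocol and SAP*

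**What the plan says.** Section 5.6.2 adds mortality and "health service utilization including hospitalizations (during study period), emergency room visits, and changes of dwelling to an assisted living environment" to the secondary outcomes. It gives no start, end or per-patient length for the period, and says of the data: "These will be collected with the COPD & Frailty – baseline, 6-month, and 12-month online surveys".

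Section 5.7.1 states that "the association between frailty and health service utilization (hospitalization, emergency room visit) and mortality will be analyzed with multivariable logistic regression". The plan has no person-time term, censoring rule, competing-risk method or composite with death. It has no rule for coding a patient who dies or leaves before an event.

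Four places bear on how long each patient is observed:

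- Section 5.3 schedules contacts per patient: "Prior to the scheduled 6-month or 12-month follow-up visit, the study team will send an e-mail to patient".
- Section 5.1 describes "A prospective cohort study at The Ottawa Hospital (TOH) over two years".
- Section 6.0 recruits at the "General campus, obtain consent (November 2022 to March 2024"), places all data collection in that same span, and dates the analysis to March 2024.
- Section 5.4 expects recruitment to take 6 months, and section 10.3 expects 12.

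Health care utilisation is part of Objective 1.

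**The concern.** A yes/no outcome in a logistic model is interpretable when everyone is observed for the same time, or when the plan says how shorter observation is handled. Neither holds here, and shorter observation is foreseeable for three reasons.

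- **Death.** The top exposure category includes CFS 8, which Figure 1 describes as completely dependent and near the end of life. Sections 1.0 and 2.0 also link frailty with mortality. The exposure therefore drives the event that prevents later admission.
- **Withdrawal.** Section 8.2 offers gift cards and personal contact to reduce losses, but no analysis rule for those that occur.
- **Calendar cut-off.** On the section 6.0 dates, late entrants are observed for less than 12 months. Section 5.4 recruits until each category reaches its minimum, and section 8.1 expects difficulty with severely frail patients, so the frailest could enter last.

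At stake is the frailty contrast for the utilisation part of Objective 1. Two analysts following this text could code the same patients differently and reach materially different odds ratios. The problem would remain with perfect ascertainment of events and a small model.

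**Working it through.** **The plan's own figures.** No event rate, power or sample size is given for these outcomes, so there is nothing to reproduce for them. The only sample size, 64 to 84 in Appendix 1, is for the SGRQ-C regression. It reproduces exactly (N = 84, power 0.804; N = 64, power 0.801) and is unaffected.

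**Step 1. Observation time on the section 6.0 dates.** November 2022 to March 2024 is A = 16 to 17 months. Assume uniform accrual, a data cut at the end, and observation capped at 12 months.

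- Share completing 12 months = (A − 12)/A: 4/16 = 25%; 5/17 = 29%.
- Share reaching 6 months = (A − 6)/A: 10/16 = 63%; 11/17 = 65%.
- Mean observation = [12(A − 12) + 72]/A: 120/16 = 7.5 months; 132/17 = 7.8 months.

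With the same cut but a shorter accrual starting in November 2022, the share completing 12 months is 33–42% for 12-month accrual (section 10.3) and 67–83% for 6-month accrual (section 5.4).

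**Step 2. Death before admission, full 12 months for all survivors.** The rates are assumptions; the documents give none. Hospitalisation hazard h is 0.2 per year in vulnerable and 0.6 in severe patients (rate ratio 3). Death hazard d is 0.03 in vulnerable patients and 0.25 or 0.5 in severe patients, that is, 12-month mortality 1 − exp(−0.25) = 22% or 1 − exp(−0.5) = 39%. Hazards are constant and independent.

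Risk of an observed admission = h/(h + d) × [1 − exp(−(h + d))].

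| Case, deaths without admission coded 'no' | Vulnerable | Severe | Odds ratio |
|---|---|---|---|
| No deaths in either group | 0.181 | 0.451 | 3.71 |
| 22% severe-group mortality | 0.179 | 0.404 | 3.12 |
| 39% severe-group mortality | 0.179 | 0.364 | 2.63 |

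**Step 3. Same patients, deaths without admission dropped instead.** The comparison is then admitted against alive and never admitted, the latter being exp(−(h + d)).

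- Vulnerable odds: 0.179/0.795 = 0.225.
- Severe odds at 22% mortality: 0.404/0.427 = 0.946, so the odds ratio is 4.2.
- Severe odds at 39% mortality: 0.364/0.333 = 1.093, so the odds ratio is 4.9.

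The unstated coding rule alone moves the result between 3.1 and 4.2, or between 2.6 and 4.9, while the rate ratio stays at 3.

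**Step 4. Withdrawal coded 'no'.** This uses a second set of assumptions: 12-month admission risk absent death 0.25 against 0.40 (odds ratio 2.00), and 12-month death risk 3% against 20%. With deaths coded 'no' the odds ratio is 1.73. Adding 10%, 20% or 30% withdrawal in the severe group, also coded 'no', gives 1.62, 1.50 or 1.38.

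**The case against.** The strongest reply is that the window is effectively fixed. Outcomes are collected at surveys scheduled 6 and 12 months into each patient's follow-up. The words about the study period may only separate follow-up admissions from "previous health care service utilization (1 year prior to study enrolment") in section 5.8. On that reading staggered entry does no harm. This is fair as far as it goes. A reader might also infer that early entrants are observed for the whole calendar study, well beyond 12 months; the documents do not support that, because no contact is planned after the 12-month survey. What remains is the truncation of late entrants under section 6.0, which contradicts a full 12 months for everyone.

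Second, no text says that a death counts as not hospitalised. If that coding were chosen and follow-up were complete, it would give the real-world cumulative incidence of admission, a legitimate target for a prediction objective. Mortality is also analysed separately. This stands, but the choice has to be made and complete follow-up has to be secured; the plan does neither.

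Third, the practical weight is limited. With 30 per group, an odds ratio of 3.12 has an approximate unadjusted 95% interval of 0.95 to 10.2 (standard error of the log odds ratio 0.60). The shift from 3.71 is ln(3.71/3.12)/0.60 ≈ 0.3 standard errors. Deaths at 39% are at the high end for clinic outpatients, and at 10% severe-group mortality the odds ratio is 3.48. This bears on how serious the point is, not on whether a rule is needed.

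**Conclusion.** The point holds. As written, the plan allows unequal time at risk, partly related to frailty, and applies a model that ignores it. The calendar part depends on which section governs: it disappears if every patient has 12 months, and is large on the section 6.0 dates (25–29% completing 12 months under uniform accrual). The death and withdrawal part remains on either reading.

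A reader might infer that the planned odds ratio must understate the effect of frailty. The documents do not support this. Coding deaths 'no' lowers the odds ratio relative to a world without deaths, but 3.12 is not below the assumed rate ratio of 3, and dropping those deaths raises it. Direction and size rest on assumed rates and on a coding rule that the plan does not state.

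The point concerns secondary outcomes only. For mortality, the issue is withdrawal and truncation, not a competing event. It should be corrected before analysis, but it does not threaten the primary SGRQ-C analysis or its sample size.

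**What to change.** 1. **Section 5.6.2.** Define the window as 12 months from each patient's baseline visit. Record the dates of first hospitalisation, first emergency room visit, death and last contact; the month is enough.
2. **Sections 5.1, 5.3, 5.4, 6.0 and 10.3.** Reconcile the recruitment and follow-up periods with that window, and date the analysis accordingly.
3. **Section 5.7.1.** Analyse time to first hospitalisation, first emergency room visit and death by Cox regression, censoring at withdrawal or last contact. Treat death as a competing event for the first two. Because the objective is prediction, also report cumulative incidence by frailty category; cause-specific hazard ratios alone do not give absolute risk. Add the composite of hospitalisation or death within 12 months, so that an early death cannot count as a good outcome.

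**Cost.** Revised wording, and date fields if the follow-up surveys do not already hold them. Self-reported dates will be approximate, and hazard ratios replace odds ratios. Patients who leave early then contribute the time for which they were observed.
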